2.4 Safety population

The Safety Population includes all randomised patients who received at least one dose of study drug. In case of violation of the randomisation scheme, patients will be classified according to the treatment they actually received.

2.5 Flow chart

The study flow chart is constructed according to the CONSORT recommendations (appendix 1 CONSORT 2010 Flow diagram and check list).

All patients included will be accounted for this study flow chart.

1. Total number of patients included
2. Number of included patients with informed consent (Patient's consent date not missing)
3. Number of included patients in the run-in period (run in attribution not missing)
4. Number of randomised patients (Patient's randomisation date not missing)
5. Number of included, run-in period, randomised patients for each centre
6. Number of randomised patients who completed the study, or discontinued after randomisation and main reason
7. Number of randomised patients at each follow-up visit and length of follow-up

The frequency and percent of subjects in each population (ITT, per-protocol, and safety), overall and by treatment groups, study withdrawals, subgroups, and major protocol violations will also be presented.

3 Analysis methods

3.1 General issues for statistical analyses

Statistical software

All statistical analyses will be performed using SAS® Software version 9.4 in a Windows environment, or R software version 3.6.3.

Missing data and outliers

All efforts will be made to collect outcome data including in patients withdrawn from the trial for whichever reasons and to minimise the amount of missing data. Unless specifically indicated, missing data will not be replaced. Outliers will be discussed as to whether to be kept or set as missing prior to database lock.

Stratification and centre effect

Unless otherwise specified, the treatment effect will be estimated on the primary and secondary outcomes after adjustment on the stratification variable.

Data transformation

Analysis of continuous variables may require transformation to normalise the distributions if the latter is justified to fulfil the hypotheses of the statistical methods to be used.

Derived and computed variables

Calculated delays since randomisation will be calculated as the time elapsed since the day of randomisation (day zero).

Delays will be converted in years or months by dividing the delays by 365.25 days or 30.4375 days respectively.

Duration=Delay+1 (days)

For the patient's date of birth, if no day is entered then it will all be replaced by 15.

Some derived and computed variables (such as delays) have been initially identified, and are described later in the document. It is expected that additional derived variables may be required. The SAP will not be amended for additional variables that are not related to the primary target or key secondary target variables. Any additional derived or computed variables will be identified and documented in the SAS programs that create analysis files.

Usual statistical presentations and tests

Description of continuous variables includes the mean, standard deviation, median, 1st and 3rd quartile, and range.

Description of categorical variables includes the frequency and percentage (based on non-missing values). Description of ordered variables includes the frequency, percentage and cumulative percentage.

Unless otherwise specified, between-group differences will be tested using the Wilcoxon rank-sum test for quantitative outcomes (or Student's t-test in case of normal distribution), using Fisher's exact test for binary outcomes, and the Mantel-Haenszel Chi-square test for ordinal outcomes.

Survival estimations will be performed using the Kaplan-Meier method [3].

A two-sided P value of less than 0.05 will be considered to indicate statistical significance. Two-sided Wald 95% confidence intervals will be used, except for median difference estimated using Hodges-Lehmann method.

Unless stated, no adjustment on p values for multiple tests will be made, thus the 95% confidence intervals should be interpreted descriptively and used as a measure of precision.

3.2 Descriptive analysis

3.2.1 Demographics and baseline characteristics

Patient characteristics at visit V1 and visit V3 (randomisation visit), will be described globally in the run-in population and globally and by treatment group in the ITT and PP populations, using usual descriptive statistics.

Following the CONSORT recommendations, no statistical tests will be performed to compare the studied groups (Moher D, Hopewell S, Schulz KF, Montori V, Gøtzsche PC, Devereaux PJ, et al. CONSORT 2010 Explanation and Elaboration: Updated guidelines for reporting parallel group randomised trials. J Clin Epidemiol. 2010;2010(63):e1–37).

Demographic and baseline characteristics

Age

Sex

Current or past smoking

Diabetes

Dyslipidaemia

Hypertension

Waist circumference

Weight before and after a dialysis session

IMC

Heart rate before and after a dialysis session

Systolic and diastolic blood pressure in lying position before and after a dialysis session, first measurement and mean of second and third values.

Systolic and diastolic blood pressure in standing position before and after a dialysis session, first measurement and mean of second and third values.

History of cardiovascular disease

History of heart failure hospitalisation

EF <40 % at baseline

Left ventricular hypertrophy

History of atrial fibrillation

ECG characteristics AFib, QRS size, Cornell index, paced ...

NB: Centralized ECG results are not available in the frozen database at the time of the SAP finalisation. These variables will be analysed later on.

Disease characteristics

First renal replacement treatment

Renal transplant

Date of first renal replacement treatment

Cause of ESRD:

- Arteriolar nephrosclerosis

- Glomerulonephritis or vascular nephritis
- Diabetes
- Tubulointerstitial nephropathy
- Hereditary or polycystic cause of ESRD
- Other cause of ESRD

Being on a waiting list for renal transplantation

Haemodialysis characteristics

Last measurement of residual diuresis in mL/24h (in the last 3 months)

Weekly frequency of dialysis sessions

Haemodialysis duration

Blood flow

Maximal ultrafiltration rate

Online haemodiafiltration

Potassium concentration in dialysis bath

Calcium concentration in dialysis bath

Type of vascular access

Potassium concentration

Laboratory characteristics

Blood glucose

Calcium level

Phosphorus level

Sodium level

Total cholesterol level

High-density lipoprotein (HDL) level

Triglyceride level

C-reactive protein (CRP) level

Albumin level

Haemoglobin level

Haematocrit

Haemoglobin A1c level in case of diabetes

PTH

Kt/V urea

25-OH vitamin D level

1,25-dihydroxy vitamin D level

Ferritin level

Medications

Concomitant treatments: ACE inhibitors, ARBs, potassium-sparing diuretic (potassium chelator), loop diuretic, potassium concentration in dialysis bath, or other

Other concomitant treatments at visit V1: spironolactone, statin, betablocker, antiplatelet, anticoagulant or others...

3.2.2 Follow-up data

For ITT and PP populations, follow-up variables will be described by treatment group using usual statistical tests (cf. paragraph 3.1).

Descriptive statistics for visits V2 and V3 to final visit

Weight before and after a dialysis session

Systolic blood pressure in lying position before and after a dialysis session, first measurement and mean of second and third values

Systolic blood pressure in standing position before and after a dialysis session, first measurement and mean of second and third values

Potassium concentration before a dialysis session

Concomitant treatments: ACE inhibitors, ARBs, potassium-sparing diuretic (potassium chelator), loop diuretic, potassium concentration in dialysis bath, or other

3.2.3 Administration of the study treatment

Run-in period

On the run-in period population, the duration of run-in treatment will be described overall according to usual descriptive statistics (cf. paragraph 3.1), considering the following definition:

Run-in treatment duration =Duration between first intake at visit V1 and last medication taken.

Study treatment period

Study treatment administration will be described on ITT and PP populations by treatment group according to usual descriptive statistics (cf. paragraph 3.1), considering the following definition:

Treatment total duration =Duration between intake at randomization and last medication taken

NB: The study drug dose was not collected in the eCRF at each visit, only adaptation of doses are available. These variables will be analysed later on.

The premature drug withdrawal, duration and reason will be also described on each population.

3.2.4 End of study

For each run-in period, ITT and PP populations, total follow-up length of study and reason for early termination will be described.

Completed the entire study

End of study date and reason

3.3 Primary efficacy analysis

Statistical analysis of the primary endpoint will primarily be based on the intent-to-treat population.

3.3.1 Primary efficacy endpoint

The primary endpoint is the time from randomisation to the onset of the first adjudicated expanded MACE event: non-fatal myocardial infarction (MI), acute coronary syndrome (ACS), hospitalisation for heart failure, non-fatal stroke, or cardiovascular death. Events were adjudicated and confirmed by an independent clinical event adjudication committee.

The full available follow-up time is the duration until all events are observed. Patients are censored at the date of renal transplantation. Patients that have shown no event and no renal transplant are censored at the date of the last available follow-up status (end of study or death, whichever occurred first), if any.

For analysis of time to first event, data will be expressed as two variables:

- A binary variable indicating whether any of the events included in the primary endpoint occurred, or the patient was censored.
- An integer variable for the number of days from randomisation to the first occurrence of an event (start date of the event – randomisation date + 1), or for event-free patients, from randomisation to censoring (censoring date – randomisation date + 1).

censored	date
0 (event)	Start date of the event is the first between : - Date of cardiovascular death - Date of cardiovascular event
1 (no event)	Censoring date is the first, following this order, between: - Date of renal transplantation - Date of death if not cardiovascular cause - Date of end of study alive

NB: cf. Appendix 2 eCRF data to construct the primary endpoint (to independent reprogramming)

In the case where several events comprising the primary outcome occur on the same day, CV death is prioritised over non-fatal CV event for description purposes.

3.3.2 Formal analysis

Main analysis

Experimental treatment will be compared using the statistical framework of proportional hazards survival model adjusted on treatment group (spironolactone versus placebo) and stratified or adjusted by centre (randomisation stratification variable). The outcome is described in Section 3.3.1. The proportionality assumption will be assessed by analysing Schoenfeld residuals and examining log-log survival plots. The Efron method for ties and p-value based on the Wald statistic will be used. The event rates, p-value, HR, and 95% confidence interval will be reported.

In case of evidence of non-proportionality, a cautious interpretation of the model will be encouraged, and a weighted (Kaplan-Meier or Cox) or a parametric model event rate estimate will be emphasised.

Kaplan-Meier estimates of the cumulative proportion of patients with event will be calculated and plotted, for the composite endpoint and for each event types of the primary endpoint. The plot will include the number of subjects at risk for each treatment group over time.

Depending on the heterogeneity of the center effect and conditional on a sufficient number of patients by centre, a frailty proportional hazard regression [4, 5, 6] could be fitted, with the centre as random effect and treatment group as fixed effect. Random effect is used to account for correlation between observations within each centre and assumes a single hazard baseline function per centre.

If the number of randomised patients per centre is too low, they will be clustered according to their similarity in ARDS patients, or the number of included patients (for example “Limoges” vs. “others”) in 2 or more groups in order to sustain the hypothesis .

If no heterogeneity is observed, an unadjusted on centre Cox proportional hazard regression will be fitted.

Component of the primary endpoint:

The contribution of each component of the primary endpoint to the overall treatment effect will be examined. The first event of each given type of event will be included, irrespective of any preceding non-fatal event of a different type. Consequently, the sum of the number of patients with events in the component analysis will be larger than the number of patients with composite events. Methods similar to those described for the primary analysis will be used to separately analyse the time from randomisation to the first occurrence of each component of the primary composite endpoint.

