Any post-hoc exploratory analyses completed to support the planned study analyses, which were not identified in this SAP, will be documented and reported in appendices to the CSR. Any results from these unplanned analyses will also be clearly identified in the text of the CSR.

1 Study rationale and objectives

Chronic kidney disease (CKD) is a public health priority. The latest European data show an incidence of end-stage renal disease (ESRD) requiring renal replacement therapy of 118 per million inhabitants/year, a prevalence of 630 per million. The unadjusted mortality rate is 29% at 2 years and 52% at 5 years. ESRD is associated with increased cardiovascular (CV) morbidity and mortality (2 to 10 times that of a population with normal renal function). Heart disease is the leading cause of mortality in patients on haemodialysis (HD) (42% of total mortality). Despite these alarming observations, this syndrome remains the poor relation of CV prevention. Very few treatments are evidence-based and CKD patients on HD are usually excluded from CV prevention trials. Aside from two positive studies among ESRD HD patients with heart failure and severely impaired left ventricular ejection fraction (stages III-IV) using renin angiotensin aldosterone system (RAAS) blockers (beta-blocker carvedilol, or a combination of angiotensin converting enzyme inhibitor (ACE-I) with an angiotensin II receptor antagonist (ARA-II) telmisartan), two morbidity-mortality studies developed by the CIC-P Nancy, the designer of the present project, and specifically including ESRD HD patients, have showed on the one hand that a statin had no effect and, on the other, that an ACE-I had a positive effect (undersized study, generating a trend of efficacy). Another study conducted in HD diabetics showed that another statin had no effect. These limited and inconclusive findings make further studies by the pharmaceutical industry unlikely in the coming years. In order to avoid that HD patients, often excluded from CV morbidity-mortality trials, remain without evidence-based therapeutic resources and continue to present unacceptable CV morbidity and mortality rates, institutionally-sponsored trials are needed. Our group has significant experience in morbidity-mortality trials in HD.

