1.3.4 Sample size determination

Assuming the following conditions:

- An annual event probability of events of 0.18 in the placebo arm (corresponding to an incidence of 19.84 per 100 person-years)
- A 30% reduction of this annual event probability in the spironolactone arm (active treatment), hence a probability of 0.126 (corresponding to an incidence of 13.46 per 100 person-years)
- A statistical power of 80% ($\beta = 20\%$)
- A bilateral test with a type-1 error rate α of 5%
- A premature study discontinuation rate (early drop-out) of 10%

A total number of **750 randomised patients (375 per arm)** to follow over 2 years in average is required to analyse the treatment effect with an exponential survival model. Considering early drop-out of 10% before randomisation, **825 patients** should be included at run-in phase.

[figure not shown]

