3.3.5 Sensitivity analysis

The following sensitivity analyses will be performed on the primary composite endpoint:

- **Analysis using the PP analysis set**

- **Informative censoring**

In the primary survival analysis, renal transplantation could prevent the observation of the primary endpoint, and therefore is an informative censoring.

Renal transplant patient characteristics will be described. In addition, time to renal transplantation will be analysed to identify if this censoring process changes the “at risk” population in the primary survival model. Hence a competing risk framework could be used to verify the impact on the model estimations.

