3.4.4 Secondary endpoint part 2-c

Survival time without a major cardiovascular event: non-fatal MI, acute coronary syndrome, hospitalization for heart failure, non-fatal stroke, or cardiac arrest resuscitation (Diagnostic or MedDRA codage, EI_date (Table EI)) will be analysed using a similar methodology to that of the main analysis of the primary composite endpoint. .

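### Kaplan-Meier curves that censor non-CV death will overstate the event proportions reported for the primary endpoint and its components; separately, the label and event list of endpoint 2-c disagree

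*SAP*

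**What the plan says.** The censoring table in section 3.3.1 ends follow-up without an event at the earliest of renal transplantation, end of study alive, and "Date of death if not cardiovascular cause". The text above the table and the programming rules in Appendix 2 agree with it.

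For absolute risk, section 3.3.2 states: "Kaplan-Meier estimates of the cumulative proportion of patients with event will be calculated and plotted, for the composite endpoint". The same sentence extends this to each event type of the primary endpoint.

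Competing risks appear only in section 3.3.5, under informative censoring. The reasoning there is that "renal transplantation could prevent the observation of the primary endpoint, and therefore is an informative censoring", and a competing-risk framework is offered as something that could be used. Non-CV death is not mentioned.

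Section 3.4.4 defines endpoint 2-c as "Survival time without a major cardiovascular event: non-fatal MI, acute coronary syndrome, hospitalization for heart failure, non-fatal stroke, or cardiac arrest resuscitation", to be analysed by methods like those for the primary endpoint. Section 1.2 (part 2, item c) gives it an event-free-survival label with essentially the same event list. Neither list contains a death.

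**The concern.** A patient who dies of a non-CV cause can no longer have a primary event. Kaplan-Meier treats that patient like one whose follow-up merely stopped, and so lets those still at risk stand in for the dead. The result is the risk in a hypothetical population in which nobody dies of other causes, not the proportion of patients who have the event. The quantity named in 3.3.2 and its estimator therefore do not match.

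The argument that 3.3.5 applies to transplantation holds at least as strongly for death, yet death is left out. The curves could also become prominent: if hazards are non-proportional, 3.3.2 gives emphasis to an event-rate estimate, and a weighted Kaplan-Meier estimate is one of the options.

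For 2-c, two programmers could build different endpoints from the same text.

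**Working it through.** **Inputs from the SAP**
- Section 1.3.4, placebo: "An annual event probability of events of 0.18 in the placebo arm (corresponding to an incidence of 19.84 per 100 person-years".
- Section 1.3.4, spironolactone: "hence a probability of 0.126 (corresponding to an incidence of 13.46 per 100 person-years".
- Section 1: "The unadjusted mortality rate is 29% at 2 years and 52% at 5 years", with heart disease accounting for 42% of deaths.

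**Check that the event rates are read correctly**
- Hazards: −ln(1 − 0.18) = 0.1984 and −ln(1 − 0.126) = 0.1347 per year; hazard ratio 0.679.
- Events needed (Schoenfeld; 80% power, two-sided 5%): 4(1.960 + 0.842)² / (ln 0.679)² ≈ 209.
- Two-year event probabilities: 1 − 0.82² = 0.328 and 1 − 0.874² = 0.236; mean 0.282.
- N = 209 / 0.282 ≈ 742, against the stated 750. Exponential-model formulas give 757 to 761 and Freedman's gives 763. The plan's figure reproduces.

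**Assumed competing hazard**
- All-cause: −ln(1 − 0.29) / 2 = 0.171 per year.
- Non-CV: (1 − 0.42) × 0.171 = 0.099 per year. This takes the heart-disease share as the whole CV share.

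**Formulas** (constant, independent hazards; event hazard l, competing hazard m, time T)
- One minus Kaplan-Meier: 1 − exp(−lT).
- Cumulative incidence: l/(l + m) × [1 − exp(−(l + m)T)].

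**Composite endpoint, m = 0.099**

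| | 1 − KM | Cumulative incidence |
|---|---|---|
| Placebo, 2 years | 32.8% | 29.9% |
| Spironolactone, 2 years | 23.6% | 21.5% |
| Risk difference, 2 years | 9.1 points | 8.4 points |
| Placebo, 4 years | 54.8% | 46.4% |
| Spironolactone, 4 years | 41.7% | 35.0% |
| Risk difference, 4 years | 13.1 points | 11.4 points |

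Worked case, placebo at 2 years: 0.1984/0.2978 × [1 − exp(−0.5955)] = 0.666 × 0.449 = 0.299. A simulation of 400,000 placebo patients gave 32.8% and 29.9% at 2 years, and 54.9% and 46.5% at 4 years.

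The main SAP plans 2 years of follow-up on average. The 4-year rows are shown because the quality-of-life SAP (section 3) gives an average of 4 years.

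**Range.** For m from 0.03 to 0.15 per year, the placebo overstatement is 0.9 to 4.2 points at 2 years and 2.8 to 12.0 points at 4 years.

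**Non-fatal events, illustration**
- CV death hazard: 0.42 × 0.171 = 0.072. Non-fatal hazard: 0.198 − 0.072 = 0.127 (unrounded 0.1265).
- With all death competing (0.171), 2 years, placebo: 1 − KM is 22.4% and cumulative incidence is 19.1%.
- Relative overstatement: 22.4/19.1 gives about 17%, against about 10% for the composite (32.8/29.9).

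**Endpoint 2-c, same hazards.** If death is a failure, the 2-year failure proportion is 1 − exp(−2 × (0.1265 + 0.1712)) = 45%. If death is censored, it is 22%. The two readings give very different endpoints.

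**The case against.** **The confirmatory result is the Cox model.** This stands. Censoring non-CV death yields a cause-specific hazard ratio, which is a legitimate target. A reader might infer that the primary hazard ratio or p-value is wrong; the documents give no ground for that.

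**Competing death is covered elsewhere.** This stands in part. Non-CV death is analysed in 2-a, all-cause death ranks first in the win ratio, and 2-b combines non-fatal events with death. An imbalance in deaths between arms would be seen, but none of these analyses corrects the primary curves.

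**The bias does not flatter the drug.** This largely stands. A reader might infer that absolute results will look too favourable. In fact each arm's risk is reported too high. The risk difference would be exaggerated in the drug's favour only if the drug works, and the analysis sections plan no risk difference or number needed to treat for the primary endpoint.

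**Endpoint 2-c may already count death.** Survival without an event can be read as failing at death. Likeness to the primary analysis does not settle it, because the primary counts CV death. The adverse-event table cited in 3.4.4 does not settle it either, because 3.5.1 also lists that table as a source for deaths. A reader might infer that patients who die are censored as event-free; the SAP never says so. What remains is that the label and the event list disagree, in an endpoint meant only for hypothesis generation.

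**Cumulative incidence has its own drawback.** This stands. It falls as competing death rises: at 2 years on placebo, 32.8% with no non-CV death, 29.9% at a hazard of 0.099 and 28.6% at 0.15. Under independence, one minus Kaplan-Meier does not move.

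**Conclusion.** The point holds for the absolute risks of the primary endpoint and its components. As written, the plan labels one quantity and estimates another, and the estimate is too high in both arms whenever competing deaths precede later events. That direction does not depend on the values assumed.

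The size does. At the main SAP's 2-year horizon it is about 3 points on placebo (0.9 to 4.2 over the range shown), and about 8 points at 4 years. These figures assume constant independent hazards, background dialysis mortality applied to trial patients, 58% of deaths being non-CV, and equal non-CV mortality in both arms. Stroke or other vascular deaths would lower the non-CV share. Renal transplantation acts in the same direction if treated as a competing event, but the SAP gives no transplantation rate, so no figure is put on it.

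For 2-c the conclusion is narrower: the definition is ambiguous and must be settled. This is a correction to reporting and specification, and it does not threaten the primary test.

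**What to change.** - **3.3.2:** keep the cause-specific Cox hazard ratio. Replace one minus Kaplan-Meier with Aalen-Johansen cumulative incidence. For the composite, non-CV death competes; for each component, all other deaths compete. Handle renal transplantation in the same way.
- **3.3.5:** make the competing-risk sensitivity analysis definite, and include non-CV death as well as transplantation.
- **Display:** show the incidence curves beside the cumulative incidence of non-CV death (2-a), because they will also reflect any difference between arms in competing death.
- **1.2 and 3.4.4:** reconcile the label and definition of 2-c. Either state that death counts as a failure, and which deaths, or rename the endpoint and treat death as a competing event.

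The cost is SAP wording and standard software. Reported event percentages will be lower than under the present plan.

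### Section 3.3.2 leaves the handling of centre in the primary Cox model open, so the 5% level of the trial's first test is not guaranteed

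*SAP*

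**What the plan says.** All of the following stands under the main analysis in SAP section 3.3.2, not under the sensitivity analyses in 3.3.5.

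- The starting model is a proportional hazards model with treatment group, "stratified or adjusted by centre (randomisation stratification variable", reported with a Wald p-value. The plan does not choose between stratifying and adjusting.
- A frailty model with centre as random effect is optional. It depends on centre heterogeneity and on centres being large enough; neither condition is quantified.
- If centres are too small, "they will be clustered according to their similarity in ARDS patients, or the number of included patients", into two or more groups. The size that counts as too small and the number of groups are left open.
- "If no heterogeneity is observed, an unadjusted on centre Cox proportional hazard regression will be fitted". No test or cut-off defines the absence of heterogeneity.
- Under non-proportional hazards the Cox model is to be read with caution, and a weighted estimate "or a parametric model event rate estimate will be emphasised".

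Section 3.1 sets the threshold: "A two-sided P value of less than 0.05 will be considered to indicate statistical significance". Section 3.4.1 puts the primary outcome first in a hierarchical procedure, followed by the win-ratio endpoint. The Introduction plans a blinded review meeting before database lock but does not give it the choice of primary model.

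**The concern.** Two competent statisticians could follow 3.3.2 faithfully and report different primary p-values. Centre heterogeneity in hazard can only be judged from event data, and the Introduction places the analyses after database lock. As written, the handling of centre can therefore depend on outcome data, and the factor on which randomisation was stratified can be dropped, with no rule to show later that the choice was neutral.

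The consequences go beyond one table. The p-value opens or closes the win-ratio test. Section 4 requires a second biostatistician to analyse the primary endpoint independently, which needs one defined model. The quality-of-life plan (its section 4, variables to be constructed) takes over whatever centre grouping the principal analysis uses. In a borderline result, the choice of model would be the first thing challenged.

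**Working it through.** **1. What the sample size assumes.** Inputs from SAP 1.3.4: annual event probabilities 0.18 and 0.126, 80% power, two-sided 5%, two years of follow-up on average, 750 randomised.

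- Rates, −ln(1−p): 0.1985 and 0.1347. HR = 0.1347/0.1985 = 0.679.
- Events (Schoenfeld): 4 × (1.960 + 0.842)² / (ln 0.679)² = 209.
- Two-year event probabilities: 1 − 0.82² = 0.3276 and 1 − 0.874² = 0.2361; mean 0.2819.
- N = 209/0.2819 ≈ 742, close to the stated 750. Power at 750 is 80.5%.

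The plan's figure reproduces as one two-sided 5% test. Nothing is set aside for a choice among models.

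**2. Null simulation of the permitted centre handlings.** The SAP gives no number of centres, centre variance or block size, so these are assumptions. 750 patients; common rate 0.166 per year; dropout hazard −ln(0.9)/2 = 0.0527 per year; follow-up uniform over 1 to 3 years; permuted blocks of 4; 25 or 60 unequal centres; log-normal centre variance as shown. There were 4000 trials per column, so the Monte Carlo standard error is √(0.05 × 0.95/4000) ≈ 0.3 points. Entries are rejection rates in %, except the last row.

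| Analysis | 25 centres, var 0 | 60, var 0 | 60, var 0.1 | 60, var 0.3 |
|---|---|---|---|---|
| Unadjusted | 4.60 | 4.78 | 4.50 | 4.40 |
| Centre-stratified | 4.45 | 4.78 | 4.80 | 4.70 |
| Frailty | 4.83 | 4.85 | 4.80 | 4.75 |
| Centre as fixed effects | 5.00 | 5.83 | 5.73 | 5.95 |
| Pooled: largest centre vs others | 4.50 | 4.83 | 4.42 | 4.37 |
| Pooled: size tertiles | 4.40 | 4.75 | 4.50 | 4.35 |
| Smallest p of these six | 5.70 | 6.70 | 6.90 | 6.98 |
| Fixed rule: likelihood-ratio test of centre at p<0.05, then stratified, else unadjusted | 4.62 | 4.83 | 4.88 | 4.73 |
| Same rule, then frailty, else unadjusted | 4.65 | 4.83 | 4.80 | 4.75 |
| Stratified and unadjusted disagree on significance | 1.65 | 2.40 | 2.45 | 2.55 |

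**3. A second simulation.** This used score tests, 2000 trials per scenario (standard error about 0.5 points), 30 or 60 unequal centres and a centre log-hazard SD of 0 or 0.4. The smallest p-value of three handlings (unadjusted, stratified, largest centre versus others) rejects in 5.3% to 6.5% of null trials.

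**4. Reading the figures.** Across both simulations the worst case is 5.3% to 7.0%, that is 0.3 to 2.0 points above nominal. With 60 centres, part of this comes from the fixed-effects version, which alone rejects in 5.7% to 6.0%. A heterogeneity rule fixed in advance and leading to stratified, frailty or unadjusted Cox rejects in 4.6% to 4.9%. The exposure therefore comes from the missing rule, not from looking at heterogeneity as such.

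**The case against.** The strongest reply is that nothing in 3.3.2 says the model is picked by its treatment p-value. The stated triggers for changing the handling of centre are heterogeneity and centre size. Both are nuisance features that can be judged on data pooled over arms, and size needs no outcome data. The candidate models are highly correlated, and stratified and unadjusted Cox disagree in only about 1.7% to 2.6% of null trials. All of this stands. It is why the conclusion is that the level is not guaranteed, and not that it is breached. It does not supply the missing test, cut-off or order, or a statement that the choice is made blind.

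A reader might also infer four stronger things that the document does not support.

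- *Section 3.3.2 contradicts 3.1.* Section 3.1 does say that "the treatment effect will be estimated on the primary and secondary outcomes after adjustment on the stratification variable", but that sentence carries an exception for cases specified otherwise, and 3.3.2 is such a case.
- *Weighted or parametric models offer further routes to significance.* If they could supply the p-value, the simulated error would be about 10.0% to 10.8%. But the clause names an event-rate estimate to be emphasised and no replacement test; the Wald p-value remains the one specified.
- *The primary is the only confirmatory test.* The win ratio is in the same hierarchy; the primary is its first step.
- *The ARDS wording blocks pooling.* The same sentence offers the number of included patients as an alternative, so pooling can proceed. The phrase is an error to correct, not evidence of inflation.

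**Conclusion.** The point holds as a gap in the specification of the primary test. Section 3.3.2 permits five ways of handling centre with no rule to choose among them, no commitment to choose blind to treatment, and one criterion that has no meaning in this population. The 5% level of the first test in the hierarchy, and so of the gate to the win ratio, is not guaranteed by the text.

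The size is modest: about 5.3% to 7.0% if the most favourable version were always reported, against 4.4% to 4.9% for a single stratified, frailty or unadjusted model. The upper figures rest on 60 assumed centres, on assumed centre variances and block size, and on worst-case selection; they do not forecast how the trial will be analysed. The gap is worth closing because it concerns the primary p-value and closing it takes a few sentences.

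**What to change.** Before unblinding, amend 3.3.2 as follows.

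1. Name one primary model, for example Cox with treatment as the only covariate, stratified by centre.
2. Pool centres below a stated number of randomised patients by size only, from a list frozen before unblinding. Delete the ARDS criterion.
3. State that the Wald p-value of this model alone decides the primary claim and the gate in 3.4.1.
4. Replace the switch to an unadjusted model by labelling the unadjusted and frailty models as sensitivity analyses. A heterogeneity rule with a stated test and cut-off, applied blind to treatment and leading to stratified, frailty or unadjusted Cox, would also hold 5% if the sponsor prefers it.
5. State that weighted or parametric estimates under non-proportional hazards are supportive and do not replace the primary p-value.

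The cost is wording, plus some information lost to stratification. The second simulation gives information ratios, stratified to unadjusted, of 0.95 with 30 centres and 0.91 with 60, a loss of about 5% to 9%. At 750 patients, expected events are 750 × 0.2819 = 211.4 and the expected z is √(211.4/4) × |ln 0.679| ≈ 2.82. Multiplying by √0.95 or √0.91 gives 2.75 or 2.69, so power falls from 80.5% to roughly 78% or 77%. Pooling small centres recovers part of this.
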